4.1 General approach

Point estimates and 95% confidence intervals (based on Wilson’s score method) of sensitivity and specificity will be derived on based on the following definitions:

		Reference standard classification		
		Positive	Negative	Total
Case prediction	Predicted positive	a	b	(a + b)
	Predicted negative	c	d	(c + d)
	Total	(a + c)	(b + d)	(a + b + c + d)
	a = True Positives, b = False Positives c = False Negatives d = True Negatives		Sensitivity = $a / (a + c)$ Specificity = $d / (b + d)$	

Table 1 Classification metrics

4.2 Analysis of the primary outcome(s)

The primary objectives 1.1, 1.2 and 1.3 will be analysed with the methodology described in section 4.1.

Outcome 1.1

Estimates of sensitivity and specificity of Xpert MTB/XDR will be calculated, for INH and ETH resistance detection with phenotypic DST and *katG*, *fabG1*, *ahpC* and *inhA* sequencing results as a composite reference standard (see Appendix). This outcome will be evaluated on the PP population.

Outcome 1.2

Estimates of sensitivity and specificity of Xpert MTB/XDR will be calculated, for fluoroquinolone resistance detection, with phenotypic DST and *gyrA* and *gyrB* sequencing results as a composite reference standard (see Appendix). This outcome will be evaluated on the PP population.

Outcome 1.3

Estimates of sensitivity and specificity of Xpert MTB/XDR will be calculated, for second-line injectable resistance detection, with phenotypic DST and *rrs* and *eis* sequencing results as a composite reference standard (see Appendix). This outcome will be evaluated on the PP population.

Outcome 1.4

Assess Xpert MTB/XDR operational aspects and ease of use, including Xpert MTB/XDR non-determinant rates.

4.3 Analysis of the secondary outcome(s)

Outcome 2.1

Direct performance versus performance on cultured samples:

- Estimates of diagnostic performance for each drug split by specimen type used for Xpert MTB/XDR (sputum or culture)

Performance between sites:

- Estimates of diagnostic performance for each individual site (India-NITRD, India-Hinduja, Moldova, and South Africa)

Performance by smear result:

- Estimates of diagnostic performance by smear gradation (smear negative, scanty, +1, +2, +3)

Performance by gene target

- Count of the number of times resistance was detected by the assay when a mutation was present in the gene region (NGS) for each gene target (*katG*, *inhA*, *ahpC*, *fabG1*, *gyrA*, *gyrB*, *rrs*, *eis*)

Performance compared to Hain MTBDR*plus/sl*

- Estimates of diagnostic performance for INH by Xpert MTB/XDR vs. Hain MTBDR*plus*
- Estimates of diagnostic performance for ETH by Xpert MTB/XDR vs. Hain MTBDR*plus*
- Estimates of diagnostic performance for FQ by Xpert MTB/XDR vs. Hain MTBDR*sl*
- Estimates of diagnostic performance for AMK/KAN/CAP by Xpert MTB/XDR vs. Hain MTBDR*sl*

Performance by patient HIV status:

- Estimates of diagnostic performance by HIV status (positive and negative)

Performance by patient pre-treatment status:

- Estimates of diagnostic performance by patient report of previous treatment for TB (yes and not)

Performance as reflex test to Ultra or MTB/RIF assay

- Estimates of diagnostic performance for each drug split by which test was used upfront (Ultra or MTB/RIF)

5 Baseline descriptive statistics

Descriptive statistics tables will be generated to summarize the characteristics of the participants. The number of participants included and excluded will be reported. Among the included participants, the information will be broken down by site, gender, and age group.

Results will be reported either in absolute numbers (e.g. number of subjects in a group) or summarized by mean, median, standard deviation, minimum, maximum and quartiles.

6 Planned interim analyses

Once 200 clinical samples have been tested by Xpert MTB/XDR both directly on the clinical sample and on the culture isolate, and have returned NGS results for all drugs tested, an interim analysis will be conducted. The diagnostic sensitivity and specificity of the Xpert MTB/XDR assay will be estimated against NGS for each drug evaluated, including for important sub-groups as detailed in Table 2.

The results will serve as an early indicator of Xpert MTB/XDR accuracy in the clinical trial. If performance estimates fall outside of the presented confidence intervals for resistance detection (Table 2), the Data Monitoring Committee (DMC) will review all data for accuracy and consistency. Additionally, the sponsor may conduct a monitoring visit to one or more sites to ensure adherence to SOPs and effective data management.

7 Additional sub-group analyses

Subgroups analyses, and definitions of subgroups, are described in section 4.3. No additional subgroup analyses will be performed.

8 Multiple comparisons/multiplicity adjustments

No multiple testing of statistical hypotheses is going to be performed.

9 Exploratory analyses

No exploratory analyses will be performed.

10 Sample size

To achieve the targeted precision for accuracy estimates, it is estimated that 760 samples will need to be tested for this study, with a final 284 MTB-positive and an additional 316 RIF-resistant samples tested by Xpert MTB/XDR and all reference standards and comparators, i.e. a total of 600 specimen results available for analysis. The desired precision for the accuracy estimates was chosen to achieve high confidence in the estimates for Xpert MTB/XDR resistance detection when considering evidence from both the 'external laboratory validation' (phase I) and the clinical trial (phase II). The sample size is detailed below in Table 2.

		n	Point estimate (95%CI) *	Total width of CI *
INH	Sensitivity	395	90% (86, 93)	7%
	Specificity	205	98% (95, 99)	4%
FQs	Sensitivity	93	90% (82, 95)	13%
	Specificity	507	98% (96, 99)	3%
AMK	Sensitivity	34	90% (74, 97)	23%
	Specificity	566	98% (96, 99)	3%
KAN	Sensitivity	71	90% (80, 96)	16%
	Specificity	529	98% (96, 99)	3%
CAP	Sensitivity	34	90% (74, 97)	23%
	Specificity	566	98% (96, 99)	3%

Table 2 Sample size

* 95%CI based on Wilson's score method (as recommended by Newcombe et al. as well as CLSI/FDA) using continuity correction.

11 Minimization of error and bias

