3.2 Scientific Rationale for Study Design

The current study is part of a two-phase project.

- Phase 1 (the current study) is an analytical study to validate and expand upon the Xpert MTB/XDR analytical data that the manufacturer (Cepheid, Sunnyvale, California) has compiled for internal validation, CE-IVD marking and/or other regulatory purposes.
- Phase 2 is a clinical study to determine the diagnostic accuracy at intended settings of use.

The two phases will provide complementary pieces of evidence to address the study objectives.

The main purpose of this clinical study is to confirm accuracy estimates from the external laboratory validation and ensure that Xpert MTB/XDR diagnostic performance characteristics will be consistent at sites of intended use. Assay performance when testing sputum samples (direct testing) and cultured isolates (indirect testing), assay performance compared to the Hain MTBDR*plus* and MTBDRs/ (Hain Lifesciences GmbH) line probe assays (LPAs), and assay error and failure rates and device operational characteristics will also be assessed during this phase of the study.

In order to address clinical study objectives quickly and efficiently, this study will first assess Xpert MTB/XDR performance for Xpert MTB/RIF MTB-positive samples from patients prospectively enrolled in the study. Focusing the study on Xpert MTB/RIF MTB-positive samples is in line with the intended use of the assay as a reflex, or follow-up, test to any Xpert MTB/RIF or Ultra MTB-positive result. This will also allow for an assessment of assay performance for INH resistance detection among all MTB-positive samples including INH mono-resistant, as this population might be different from a largely RIF-resistant population. However, to ensure numbers are adequate for an assessment of Xpert MTB/XDR assay performance for second-line resistance detection, once sufficient MTB-positive, RIF-sensitive samples have been tested, a subset of solely Xpert RIF-resistant samples will be tested until enrolment targets are met (see section 9.1 and Appendix 4: Sample Requirement to Achieve Target Sample Size).

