9.2.3 Additional Characteristics Assessed

Secondary analyses will investigate assay diagnostic performance between important subgroups, including: Xpert MTB/XDR direct versus indirect performance (on direct versus cultured samples), performance between sites, by smear result, by gene target, performance compared to Hain MTBDR*plus* and MTBDR*sl* assays, performance by reflex test to Xpert MTB/RIF or Ultra result, and performance by patient HIV and pre-treatment status. Detailed definitions for diagnostic test results are given in Appendix 5: Definitions of Diagnostic Test Results.

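### Consistent performance across sites is part of the stated main purpose, but the SAP plans only four separate site estimates and no between-site contrast

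*SAP*

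**What the plan says.** Protocol 3.2 gives the main purpose in two parts: confirm the accuracy estimates from the laboratory validation, and "ensure that Xpert MTB/XDR diagnostic performance characteristics will be consistent at sites of intended use". Protocol section 2 lists performance between sites under secondary objective 2.1. Of the secondary work, Protocol 9.2.3 says: "Secondary analyses will investigate assay diagnostic performance between important subgroups", and it includes sites among those subgroups. Protocol 9.2.4 names chi-squared first among the methods for the secondary endpoint but ties it to no comparison.

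SAP 4.3, under performance between sites, has a single line: "Estimates of diagnostic performance for each individual site", naming four sites (two in India, one in Moldova, one in South Africa). By SAP 4.1 these are "Point estimates and 95% confidence intervals (based on Wilson’s score method) of sensitivity and specificity". Chi-squared appears nowhere in the SAP. Section 8 states: "No multiple testing of statistical hypotheses is going to be performed". Section 9 states: "No exploratory analyses will be performed". Neither document defines consistency between sites or gives a planned number per site. The primary accuracy analysis pools all sites (Protocol 9.2).

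**The concern.** A question about consistency is a question about differences, and four separate estimates do not estimate a difference. The two documents also disagree: one lists a test with no stated target, the other lists none. With no contrast planned, the natural reading of the site table is to see whether the intervals overlap. Overlap is a conservative check even with adequate numbers, and it is close to uninformative when each site has a handful of resistant samples. The risk is that wide, overlapping intervals are taken as evidence that the assay performs alike everywhere, when the data could not have shown otherwise.

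**Working it through.** **1. The plan's own precision.** Table 2 (Protocol 9.1, SAP 10) reproduces with the continuity-corrected Wilson interval at 90% sensitivity: INH n = 395, 86.5 to 92.7; FQ n = 93, 81.6 to 95.0; KAN n = 71, 80.0 to 95.5; AMK and CAP n = 34, 73.7 to 97.1. These round to the stated limits. All are pooled over sites.

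**2. Per-site numbers.** The documents give no split by site. Assume an equal split over the four sites named in SAP 4.3: 395/4 ≈ 99, 93/4 ≈ 23, 71/4 ≈ 18, 34/4 = 8.5 resistant samples. The Wilson interval at an observed 90% is then:

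| Drug | n per site | 95% interval | Width (points) |
|---|---|---|---|
| INH | 99 | 82.5 to 94.5 | 12 |
| FQ | 23 | 71.6 to 97.0 | 25 |
| KAN | 18 | 68.6 to 97.4 | 29 |
| AMK, CAP | 8 | about 56 to 98 | 43 |

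ETH has no row in Table 2, so its per-site precision cannot be derived.

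**3. What a site-versus-rest contrast detects.** Assume one site at p1 = 80% and the other three at p2 = 90%. The large-sample power of a two-sided 5% comparison is

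Φ{[(p2 − p1) − 1.96·√(p̄(1−p̄)(1/n1 + 1/n2))] / √(p1(1−p1)/n1 + p2(1−p2)/n2)}.

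- INH, n1 = 99, n2 = 296: p̄ = 0.875; (0.1 − 0.0753)/0.0438 = 0.56; power 71%.
- FQ, n1 = 23, n2 = 70: (0.1 − 0.1557)/0.0908 = −0.61; power 27%.
- KAN, n1 = 18, n2 = 53: (0.1 − 0.1771)/0.1029 = −0.75; power 23%.
- AMK or CAP, n1 = 8, n2 = 26: (0.1 − 0.2607)/0.1532 = −1.05; power 15%.

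Eighty per cent power for this difference needs about 125 resistant samples at the poor site.

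**4. Simulation of the actual intervals, same assumption.** The Newcombe interval for d = p̂1 − p̂2 uses the Wilson limits (l, u) of each group: lower d − √[(p̂1−l1)² + (u2−p̂2)²], upper d + √[(u1−p̂1)² + (p̂2−l2)²].

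| | INH | FQ | KAN |
|---|---|---|---|
| Newcombe contrast excludes zero | 71% | 25% | 21% |
| Poor site's interval misses the pooled interval of the rest | 44% | 7% | 5% |
| Chi-squared over four sites, 3 df | 55% | 14% | 11% |

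For INH, some pair among the four site intervals fails to overlap in about 42%. For AMK and CAP the 3-df test rejects in about 5%. With all sites truly equal, the contrast wrongly flags a given site as low in about 3% of trials, so at most 4 × 3% = 12% for any site, per drug and measure.

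**5. Range over the assumptions.**
- *Size of deficit.* With the poor site at 85%, 75% or 70%, the formula in step 3 gives INH 29%, 94% and 99%; FQ 12%, 45% and 62%; KAN 10%, 38% and 53%.
- *Unequal split (10/20/30/40%), poor site at 80%.* The one-site-against-rest chi-squared gives INH 47% if the smallest site is poor and 80% if the largest is; FQ 20% to 30%; KAN 19% to 26%; AMK/CAP 12% to 16%.
- *Large deficit (70% against 96.7%).* The Newcombe contrast flags the site in 93% (FQ) and 87% (KAN), against 51% and 26% for non-overlap of any pair.

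**The case against.** The strongest reply is that this is an estimation study and site estimates with intervals are a legitimate descriptive analysis. Four points support it.

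- The consistency phrase in Protocol 3.2 can also be read as agreement between field and laboratory performance, and between-site performance is one of eight items under a secondary objective. This tempers the weight of the point. It does not remove it, because Protocol 9.2.3 promises a comparison between sites in any case.
- A reader might infer that the SAP forbids the chi-squared test. It does not: section 8 speaks of multiple testing and does not name the test, and the protocol never assigned it to sites. The accurate word is omission.
- A reader might also infer that a poor site would be missed because the test was dropped. The figures do not support that. With a site at 80%, the 3-df test still misses it in 86% of trials for FQ and 89% for KAN. The main limit is the number of resistant samples per site.
- No passage makes interval overlap a decision rule, and because each site's estimate is reported, pooling would not conceal a poor one. Comparing a site's own interval with the planning value of 90% flags it in 86% of trials for INH, 31% for FQ and 28% for KAN. That is more often than the contrast, but it is not in the plan and it checks level, not consistency: four sites all at 80% would be flagged although they agree.

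The interim review is a partial safeguard. Protocol 9.3 extends it to the subgroups of section 2, which include sites, and estimates outside the Table 2 intervals prompt a data review. But it uses NGS alone, SAP 6 points for its subgroups to Table 2, which lists drugs and not sites, and it does not govern the final analysis.

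**Conclusion.** The point holds as a gap in the analysis and a mismatch between documents. Part of the stated main purpose has no planned between-site contrast, and the method the protocol lists is neither assigned there nor carried into the SAP. A site-versus-rest difference would be a real gain for INH (about 71% against 42% for interval non-overlap, for 80% against 90%) and a small absolute one for FQ and KAN (about 25% and 21%). For AMK and CAP it would say little. The equal four-way split and the size of the deficit are assumptions; step 5 of the working shows how far the figures move. The primary pooled estimates are not affected. The documents do not support the stronger claims that the SAP prohibits a test or that restoring one would make a poor site visible for the second-line drugs.

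**What to change.** In SAP 4.3, under performance between sites, report for each drug each site's difference in sensitivity and in specificity from the other sites combined, with a 95% Newcombe interval, labelled supportive and unadjusted. An exact test over the four sites is optional.

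State in the same place that site-level sensitivity for FQ, KAN, AMK and CAP is imprecise (about 8 to 23 resistant samples per site under an equal split), so that neither overlapping intervals nor a non-significant test may be read as evidence of consistency.

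Reword SAP 8 to acknowledge these contrasts, and align Protocol 9.2.4 by saying which comparison, if any, chi-squared serves.

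The cost is SAP wording, a matching protocol edit and one extra table from data already collected. The downside is that the table will carry little information for the second-line drugs and, being unadjusted, will sometimes flag a site by chance.

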Rapid diagnostics for second-line drug resistance detection identify mutations in the *gyrA* and *gyrB* genes⁷, associated with fluoroquinolone resistance, and *rrs* and *eis* gene regions, associated with second-line injectable resistance (with *eis* promoter mutations exclusively associated with KAN resistance)⁸. Recently, a novel GeneXpert cartridge was developed to detect mutations occurring in these genes, as well as in the *katG* and *inhA* gene regions, associated with INH resistance⁹. A Research Use Only (RUO) version of the Xpert MTB/XDR cartridge showed promising performance for INH and second-line resistance detection in a clinical evaluation study (sensitivity 92.7-98.1%; specificity 94.3-99.6%)¹⁰. The assay chemistry has since been improved and additional gene targets have been added to the assay to improve the detection of INH resistance (i.e. *fabG1* and *ahpC*).

Evidence of assay accuracy from an external laboratory validation using a well-characterized set of Mtb strains as well as from large-scale, multicentre clinical studies is needed to confirm the validity of the most recent Xpert MTB/XDR assay for INH and second-line resistance detection, and to recommend its use in diverse clinical settings. The focus of this protocol is the multicentre clinical evaluation.

2 Study Objectives and Endpoints

Objectives	Data Collected	Endpoint
Primary		
1.1 Estimate the diagnostic accuracy of the Xpert MTB/XDR assay for INH and ETH resistance detection , for a clinically diverse set of TB samples, with phenotypic DST and katG , fabG1 , ahpC and inhA	284 Xpert MTB/RIF TB-positive and 316 RIF-resistant clinical samples tested by Xpert MTB/XDR, phenotypic DST and NGS	1.1 Sensitivity and specificity estimates for INH and ETH resistance detection

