5.3.3 Reference Standard and Comparators

There is little risk of reference standard bias in this study as a composite reference standard of phenotypic DST and NGS will be used for resistance detection (Table 1). The use of both phenotypic and genotypic information will ensure high confidence in the reference standard, as certain mutations (e.g. many *eis* promoter mutations) are known to confer only low-levels of phenotypic drug resistance, and so they may not be detected by phenotypic DST at only one critical concentration. Furthermore, all molecular assays evaluated in this study detect resistance-mutations in similar gene regions, and so all mutations that are detectable by the Xpert MTB/XDR assay are generally detected by NGS and/or the Hain LPAs and vice versa.

Table 1. Composite reference standard for diagnostic performance analysis

Composite Reference Standard		
Drug of Interest	NGS of Reference Gene(s)	MGIT960 Phenotypic DST
Isoniazid	katG , fabG1 , inhA promoter, ahpC promoter	Isoniazid
Ethionamide	inhA promoter	Ethionamide

Fluoroquinolones		
Moxifloxacin	gyrA, gyrB	Moxifloxacin
Levofloxacin	gyrA, gyrB	Levofloxacin
Second-line Injectables		
Amikacin	rrs	Amikacin
Kanamycin	rrs, eis promoter	Kanamycin
Capreomycin	rrs	Capreomycin

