9.2.2 Definitions for Diagnostic Performance Analysis

TEST RESULT	DESCRIPTION
Phenotypic Drug*-resistant	Culture-positive and growth for Drug* in conventional DST testing.
Phenotypic Drug*-sensitive	Culture-positive and no growth for Drug* in conventional DST testing
Genotypic Drug*-resistant	NGS identifies mutations recognized to be associated with resistance (defined based on consultation with WHO prior to analysis)
Genotypic Drug*-sensitive	NGS identifies no mutations recognized to be associated with resistance (defined based on consultation with WHO prior to analysis)
Composite reference standard Drug*-resistant	If Phenotypic Drug*-sensitive but NGS identifies mutations recognized to be associated with Drug* resistance for the respective gene regions, the composite reference standard will be considered Drug*-resistant. If Phenotypic Drug*-resistant but NGS does not identify mutations recognized to be associated with Drug* resistance for the respective gene regions, the composite reference standard will be considered Drug*-resistant (as mutations will be assumed outside of the region sequenced).

Composite reference standard Drug*-sensitive | If Phenotypic Drug*-sensitive and NGS shows either no mutations or only mutations that are not associated with Drug* resistance for the respective gene regions.

* Drug: INH, ETH, FQ (moxifloxacin and levofloxacin for phenotypic DST), AMK, KAN or CAP

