Appendix 5: Definitions of Diagnostic Test Results

TEST RESULT	DESCRIPTION
Smear-positive	≥ 1 positive FM smear (inclusive of scanty positive smears) using WHO/IUATLD grading.
Culture-positive	LJ and/or MGIT culture growth-confirmed MTB complex.
Culture-negative	LJ or MGIT have no culture growth after >56 days and >42 days
Contaminated culture	LJ: Culture completely overgrown by bacterial or fungal contaminations within 3 weeks (discarded). In case of mixed cultures, isolated MTB colonies transferred to new LJ tube (repeat culture).
NGS INH-sensitive	Targeted NGS of katG , fabG1 , ahpC and inhA does NOT detect any mutations associated with INH resistance.
NGS INH-resistant	Targeted NGS of katG , fabG1 , ahpC and inhA detects at least one mutation associated with INH resistance.
NGS ETH-sensitive	Targeted NGS of inhA does NOT detect any mutations associated with INH resistance.
NGS ETH-resistant	Targeted NGS of inhA detects at least one mutation associated with INH resistance.
NGS FQ-sensitive	Targeted NGS of gyrA and gyrB does NOT detect any mutations associated with FQ resistance.
NGS FQ-resistant	Targeted NGS of gyrA and gyrB detects at least one mutation associated with FQ resistance.
NGS AMK-sensitive	Targeted NGS of rrs does NOT detect any mutations associated with AMK resistance.
NGS AMK-resistant	Targeted NGS of rrs detects at least one mutation associated with AMK resistance.
NGS KAN-sensitive	Targeted NGS of rrs and eis does NOT detect any mutations associated with KAN resistance.
NGS KAN-resistant	Targeted NGS of rrs and eis detects at least one mutation associated with KAN resistance.
NGS CAP-sensitive	Targeted NGS of rrs does NOT detect any mutations associated with CAP resistance.
NGS CAP-resistant	Targeted NGS of rrs detects at least one mutation associated with CAP resistance.
MTBDR _{plus} INH-sensitive	No detection of katG or inhA mutations associated with INH resistance by line probe assay (WT probe hybridization, no MUT probes hybridized).
MTBDR _{plus} INH-resistant	Detection of katG or inhA mutations associated with INH resistance by line probe assay (MUT probe hybridization or absence of WT probe hybridization).

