MTBDRs/ FQ-sensitive	No detection of gyrA or gyrB mutations associated with FQ resistance by line probe assay (WT probe hybridization, no MUT probes hybridized).
MTBDRs/ FQ-resistant	Detection of gyrA or gyrB mutations associated with FQ resistance by line probe assay (MUT probe hybridization or absence of WT probe hybridization).
MTBDRs/ AMK-sensitive	No detection of rrs mutations associated with AMK resistance by line probe assay (WT probe hybridization, no MUT probes hybridized).
MTBDRs/ AMK-resistant	Detection of rrs mutations associated with AMK resistance by line probe assay (MUT probe hybridization or absence of WT probe hybridization).
MTBDRs/ KAN-sensitive	No detection of rrs or eis mutations associated with KAN resistance by line probe assay (WT probe hybridization, no MUT probes hybridized).
MTBDRs/ KAN-resistant	Detection of rrs or eis mutations associated with KAN resistance by line probe assay (MUT probe hybridization or absence of WT probe hybridization).
MTBDRs/ CAP-sensitive	No detection of rrs mutations associated with CAP resistance by line probe assay (WT probe hybridization, no MUT probes hybridized).
MTBDRs/ CAP-resistant	Detection of rrs mutations associated with CAP resistance by line probe assay (MUT probe hybridization or absence of WT probe hybridization).
Xpert MTB/XDR Drug*-sensitive	Valid result with Drug* resistance NOT detected by Xpert MTB/XDR.
Xpert MTB/XDR Drug*-resistant	Valid result with Drug* resistance detected by Xpert MTB/XDR.
Xpert MTB/XDR Drug*-indeterminant	Valid result with Drug* resistance indeterminant.
Xpert MTB/XDR non-determinant**	No valid run result by Xpert MTB/XDR.

* Drug: INH, ETH, FQ (moxifloxacin and levofloxacin for phenotypic DST), AMK, KAN or CAP

**Xpert non-determinants: result during initial run or after repeat following an invalid result

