11.1 Enrolment and randomization procedures

Describe how enrolment will be carried out (from the clinical protocol) and add details on the randomization procedure (if applicable)

12 Case definitions

Table 3 describes the categorization of results based on test results.

TEST RESULT	DESCRIPTION
Phenotypic Drug*-resistant	Culture-positive and growth for Drug* in conventional DST testing.
Phenotypic Drug*-sensitive	Culture-positive and no growth for Drug* in conventional DST testing
Genotypic Drug*-resistant	NGS identifies mutations recognized to be associated with resistance (defined based on consultation with WHO prior to analysis)
Genotypic Drug*-sensitive	NGS identifies no mutations recognized to be associated with resistance (defined based on consultation with WHO prior to analysis)
Composite reference standard Drug*-resistant	If Phenotypic Drug*-sensitive but NGS identifies mutations recognized to be associated with Drug* resistance for the respective gene regions, the composite reference standard will be considered Drug*-resistant. If Phenotypic Drug*-resistant but NGS does not identify mutations recognized to be associated with Drug* resistance for the respective gene regions, the composite reference standard will be considered Drug*-resistant (as mutations will be assumed outside of the region sequenced).
Composite reference standard Drug*-sensitive	If Phenotypic Drug*-sensitive and NGS shows either no mutations or only mutations that are not associated with Drug* resistance for the respective gene regions.

* Drug: INH, ETH, FQ (moxifloxacin and levofloxacin for phenotypic DST), AMK, KAN or CAP

Table 3 Case definitions

13 Statistical software

The analysis will be performed using the R statistical language (version 3.4.0 or higher) on OsX, and Microsoft Excel 2018 (version 16.16 or higher).

14 References

Add required references.

15 Document history

Version	Notes / Changes
1.0	Initial version

16 Appendix

The definitions of composite reference standards are given in table 4.

DRUG RESISTANCE	COMPOSITE REFERENCE STANDARD
INH-resistant	NGS of katG , fabG1 , ahpC and inhA detects ≥ 1 mutation associated with INH resistance and MGIT culture is INH drug-resistant at the critical concentration.
ETH-resistant	NGS of inhA detects ≥ 1 mutation associated with ETH resistance and MGIT culture is ETH drug-resistant at the critical concentration.

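### SAP 4.3 credits a drug-level resistance call to every mutated gene for that drug, so co-mutated samples inflate the apparent detection of the weaker gene targets

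*SAP*

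**What the plan says.** Performance by gene target is one of the items under secondary objective 2.1 (protocol section 2). SAP 4.3 gives the whole of its analysis in one line: "Count of the number of times resistance was detected by the assay when a mutation was present in the gene region", as shown by NGS, for katG, inhA, ahpC, fabG1, gyrA, gyrB, rrs and eis. It gives no denominator, interval, rule for samples mutated in more than one gene, or drug call to be read for each gene.

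Protocol Appendix 5 defines a positive index test by drug: "Valid result with Drug* resistance detected by Xpert MTB/XDR". Neither document defines an Xpert MTB/XDR result for a single gene.

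Several genes serve one drug. For isoniazid, protocol Table 1 (section 5.3.3) lists "katG , fabG1 , inhA promoter, ahpC promoter". For the fluoroquinolones it lists gyrA and gyrB, and for kanamycin rrs and the eis promoter.

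Elsewhere the documents qualify which mutations matter. The genotypic-resistant definition in SAP Table 3 (section 12) reads "NGS identifies mutations recognized to be associated with resistance (defined based on consultation with WHO prior to analysis", and protocol Appendix 5 classes a sample as NGS INH-resistant when sequencing "detects at least one mutation associated with INH resistance". Both documents also foresee phenotypically sensitive samples in which "NGS shows either no mutations or only mutations that are not associated with Drug* resistance for the respective gene regions", and class them as sensitive. SAP 4.3 neither repeats nor cites this limit.

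**The concern.** A reader of this analysis will want to know which targets work. Protocol 1.3 says that "additional gene targets have been added to the assay to improve the detection of INH resistance", naming fabG1 and ahpC, so whether those two are picked up in their own right is an obvious use of the table. Under the stated rule, a sample mutated in katG and fabG1 and called isoniazid-resistant because of katG adds one to the fabG1 count. A target that the assay reads poorly, or not at all, can still build up detections from the company it keeps.

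Nothing else in the plan would reveal this. SAP sections 7 and 9 rule out additional subgroup and exploratory analyses, so a split between single-gene and multi-gene samples is not foreseen.

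**Working it through.** The documents state no expected count, rate or precision for this analysis, so there is no figure of the plan to reproduce. The direction of the bias follows from the definitions. Its size can only be illustrated under assumed inputs.

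**Where co-mutation can mislead.** Isoniazid pools four genes, fluoroquinolones two and kanamycin two (protocol Table 1 and Appendix 5). Capreomycin rests on rrs alone in both documents, and ethionamide on inhA alone. Amikacin rests on rrs alone in protocol Table 1 but on rrs and eis in SAP Table 4.

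**Upward bias from co-mutation.** All inputs are assumed:
- s: true detection through the gene of interest
- c: share of that gene's mutated samples that carry a second mutated gene for the same drug
- t: detection through that second gene, taken as independent of the first

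Samples mutated in this gene alone are called at rate s. Co-mutated samples are called unless both genes are missed, at rate 1 − (1 − s)(1 − t). Hence

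apparent detection = (1 − c)·s + c·[1 − (1 − s)(1 − t)] = s + (1 − s)·c·t.

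The added term cannot be negative, and for given c and t it grows as s falls, so the weaker target gains most.

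Example: of 40 samples mutated in a gene with s = 50%, 20 are co-mutated and t = 95%. The 20 single-gene samples give 20 × 0.50 = 10 detections. The other 20 give 20 × (1 − 0.50 × 0.05) = 19.5. Together that is 29.5/40 = 73.75%, against a true 50%.

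Apparent detection with t = 95%, to whole percent:

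| True s | c = 10% | c = 25% | c = 50% | c = 75% |
|---|---|---|---|---|
| 0% | 10 | 24 | 48 | 71 |
| 50% | 55 | 62 | 74 | 86 |
| 70% | 73 | 77 | 84 | 91 |
| 90% | 91 | 92 | 95 | 97 |

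**Downward bias, only if a rate over all mutated samples is formed.** Let h be the assumed share of a gene's mutated samples whose only mutation there is not resistance-associated, and suppose the assay correctly does not call them. Then apparent detection = (1 − h)·s. With s = 98% and h = 5, 10, 20 or 30%, this gives 93, 88, 78 or 69%. It runs against the co-mutation bias, so a plausible-looking figure could hide both.

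**The case against.** The strongest reply is that the SAP prescribes only a count. A reader might infer that non-associated mutations are scored as misses, but the text does not say so: a sample that the assay does not call adds nothing to a count, and becomes a miss only if someone divides by all mutated samples. The association limit also stands in SAP Tables 3 and 4 and in protocol Appendix 5, so its absence from SAP 4.3 may be an omission of wording rather than of intent. That stands. This part is a gap in specification.

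A reader might also infer that a katG-driven call must inflate inhA. That assumes the isoniazid call is the one used for inhA. Protocol Table 1 ties ethionamide to the inhA promoter alone, and Appendix 5 covers a separate ethionamide result, so the inhA row could be read from that call. The rrs row could likewise be read from capreomycin. Table 1 describes the reference genes rather than the assay's calling logic, so this does not settle the matter, but it shows that the drug call per gene is undefined.

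It is also fair that the count is informative where a single gene is mutated, that it gives an upper bound where several are, and that the bias is small if co-mutation is rare.

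None of this removes the main point for fabG1 and ahpC, which Table 1 links to isoniazid only, for gyrA and gyrB, or for eis.

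**Conclusion.** The co-mutation part holds on the documents' own definitions: a rule that counts by gene is applied to a result defined by drug, with no provision for samples mutated in several genes. The bias is upward and greatest for the weaker target. With true detection of 50% and 95% detection through the other gene, 10% to 50% co-mutation would show about 55% to 74%. These inputs, and the independence behind the formula, are assumptions; the documents give neither co-mutation nor per-gene detection rates.

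The missing association limit, denominator and drug call are gaps to close, not errors that the SAP prescribes. Nor do the documents support the conclusion that the count is uninformative; it is hard to interpret where genes are co-mutated.

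The consequence is confined to one descriptive item under objective 2.1. Primary sensitivity and specificity are assessed by drug and are unaffected, so this is a minor point.

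**What to change.** Amend the gene-target item in SAP 4.3 to:

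- restrict it to resistance-associated mutations, as settled through the WHO consultation referred to in SAP Table 3 (the table itself contains no list);
- name the drug call used for each gene, notably isoniazid or ethionamide for inhA, and amikacin, kanamycin or capreomycin for rrs;
- report detected/total, with the Wilson 95% interval of SAP 4.1, for samples in which that gene is the only one with a resistance-associated mutation for that drug;
- show co-mutated samples in a separate row.

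No new data or testing are needed. The cost is small denominators for some targets. For scale, SAP Table 2 already expects a 23-point interval for amikacin sensitivity with 34 resistant samples at 90%; at similar detection, a target with fewer single-gene samples will be less precise still. That imprecision reflects the evidence available for the target and is better shown than hidden by co-mutated samples.
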